8.3. Adverse Events, Serious Adverse Events, and Product Complaints

Investigators are responsible for monitoring the safety of participants who have entered this study and for alerting Lilly or its designee to any event that seems unusual, even if this event may be considered an unanticipated benefit to the participant.

The investigator is responsible for the appropriate medical care of participants during the study.

The definitions of the following events can be found in Appendix 3:

- AEs
- SAEs
- ADEs
- UADEs
- SADEs, and
- product complaints

These events will be reported by the participant (or, when appropriate, by a caregiver, surrogate, or the participant's legally authorized representative).

The investigator and any qualified designees are responsible for detecting, documenting, and recording events that meet these definitions and remain responsible for following up events that are serious, considered related to the study intervention or study procedures, or that caused the participant to discontinue the study (see Section 7).

Care will be taken not to introduce bias while detecting events. Open-ended and nonleading verbal questioning of the participant is the preferred method to inquire about event occurrences.

After the initial report, the investigator is required to proactively follow up each participant at subsequent visits/contacts. All SAEs will be followed up until resolution, stabilization, the event is otherwise explained, or the participant is lost to follow-up (as defined in Section 7.3). For product complaints, the investigator is responsible for ensuring that follow-up includes any supplemental investigations as indicated to elucidate the nature and/or causality. Further information on follow-up procedures is provided in Appendix 10.3.

8.3.1. Timing and Mechanism for Collecting Events

This table describes the timing, deadlines, and mechanism for collecting events.

Event	Collection Start	Collection Stop	Timing for Reporting to Sponsor or Designee	Mechanism for Reporting
AE	Signing of the ICF	Participation in study has ended	As soon as possible upon site awareness	AE eCRF

Event	Collection Start	Collection Stop	Timing for Reporting to Sponsor or Designee	Mechanism for Reporting
SAE and SAE updates – prior to start of study intervention and deemed reasonably possibly related with study procedures	Signing of the ICF	Start of intervention	Within 24 hours of awareness	SAE eCRF
SAE and SAE updates – after start of study intervention	Start of intervention	Participation in study has ended	Within 24 hours of awareness	SAE eCRF
SAE – after participant’s study participation has ended and the investigator becomes aware	After participant’s study participation has ended	NA	Promptly	SAE paper form
Pregnancy in female participants and female partners of male participants	After the start of study intervention	125 days after dose	Within 24 hours of learning of the pregnancy	Pregnancy eCRF or SAE eCRF
Product complaint associated with an SAE or might have led to an SAE	Start of study intervention	End of study intervention	Within 24 hours of awareness	product complaint form
Product complaint not associated with an SAE	Start of study intervention	End of study intervention	Within 1 business day of awareness	product complaint form
Updated product complaint information	—	—	As soon as possible upon site awareness	Originally completed product complaint form with all changes signed and dated by the investigator
Product complaint (if investigator becomes aware)	Participation in study has ended	NA	Promptly	Product complaint form

8.3.2. Adverse Events of Special Interest

Adverse events of special interest for this study include

- conjunctivitis
- herpes infection or zoster, and
- parasitic infection or an infection related to an intracellular pathogen.

If these adverse events of special interest are reported, sites will be prompted to collect additional data.

8.4. Treatment of Overdose

For this study, any dose of lebrikizumab greater than 250 mg will be considered an overdose.

The sponsor does not recommend specific treatment for an overdose.

In the event of an overdose, the investigator/treating physician should

1. contact the medical monitor immediately.
2. closely monitor the participant for any AE/SAE and laboratory abnormalities.

8.5. Pharmacokinetics

Blood samples of approximately 3 mL will be collected for measurement of serum concentrations of lebrikizumab as specified in the SoA.

A maximum of 5 samples may be collected at additional time points during the study if warranted and agreed upon between the investigator and the sponsor. The timing of sampling may be altered during the course of the study based on newly available data (for example, to obtain data closer to the time of peak serum concentrations) to ensure appropriate monitoring.

Instructions for the collection and handling of biological samples will be provided by the sponsor. The actual date and time (24-hour clock time) of each sample will be recorded.

8.5.1. Bioanalysis

Samples will be analyzed at a laboratory approved by the sponsor and stored at a facility designated by the sponsor.

Serum concentrations of lebrikizumab will be assayed CCI.
[REDACTED]. Analyses of samples collected from placebo-treated participants are not planned.

Bioanalytical samples collected to measure investigational product concentrations will be retained for a maximum of 1 year following last participant visit for the study. CCI
[REDACTED]

8.6. Pharmacodynamics

Pharmacodynamic parameters are not evaluated in this study.

8.7. Genetics

Genetics are not evaluated in this study.

A blood sample for DNA isolation will be collected from participants.

See Appendix 10.5 for information regarding genetic research.

8.8. Biomarkers

Biomarkers are not evaluated in this study.

8.9. Immunogenicity Assessments

At the visits and times specified in the SoA, venous blood samples will be collected to determine antibody production against lebrikizumab. Antibodies may be further characterized and/or evaluated for their ability to neutralize the activity of lebrikizumab. To interpret the results of immunogenicity, a venous blood sample will be collected at the same time points to determine the serum concentrations of lebrikizumab. All samples for immunogenicity should be taken predose when applicable and possible.

Immunogenicity will be assessed by a validated assay designed to detect ADAs in the presence of lebrikizumab at a laboratory approved by the sponsor. Samples may be stored for a maximum of 15 years (or according to local regulations) following the last participant's last visit for the study at a facility selected by the sponsor. Samples may also be used for development and control of an immunogenicity assay.

8.10. Health Economics

This section is not applicable for this study.

9. Statistical Considerations

9.1. Statistical Hypotheses

The primary objective of this study is to evaluate PK following administration of lebrikizumab using a PFS-NSD and an AI.

9.2. Sample Size Determination

Approximately 240 participants may be enrolled so that approximately 216 participants (108 in the lebrikizumab PFS-NSD [reference] group and 108 in the AI [test] group) complete the study.

A sample size of 108 participants per device group will provide approximately 90% power that the 90% CI of the geometric mean ratio of maximum observed drug concentration (C_{max}) and area under the concentration versus time curve (AUC) between groups will fall within equivalence range of 0.8 to 1.25. This sample size calculation was based on the assumptions that the PK parameters have log-normal distribution, the percent coefficients of variation (%CV) of C_{max} and AUC are less or equal to 30%, the expected ratio of geometric means is between 0.9 and 1.1, and the %CV are the same for participants from each device group. The 30% CV assumption is based on lebrikizumab PK data in several previous studies.

To properly evaluate AUC from time zero to infinity ($AUC[0-\infty]$), lebrikizumab concentrations must be collected through at least Day 71. To ensure that approximately 216 participants (108 in each group) provide evaluable PK data, approximately 240 participants will be enrolled and receive study drug, assuming up to 10% of the participants may not complete through at least Day 71. Participants who do not complete at least through Day 22 (a period sufficient to determine C_{max}) may be replaced. The replacement participants should be in the same weight category as the original participants.

9.3. Populations for Analyses

The following populations are defined:

Population	Description
Safety	All participants randomly assigned to study intervention and who receive study intervention. Participants will be analyzed according to the intervention they actually received.
Pharmacokinetic Analysis	All enrolled participants who received a full dose of study intervention and have evaluable PK sample.

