4.4. End of Study Definition

The end of the study is defined as the date of the last visit of the last participant in the study. Participants may be replaced to ensure that approximately 216 participants (108 in each group) complete the study (see Section 9.2).

5. Study Population

Eligibility of participants for enrollment in the study will be based on the results of screening medical history, physical examination, vital signs, clinical laboratory tests, and ECG. The nature of any conditions present at the time of the physical examination and any preexisting conditions will be documented.

The inclusion and exclusion criteria used to determine eligibility should be applied at screening only, and not continuously throughout the trial.

Screening may occur up to 28 days prior to enrollment. Participants who are not enrolled within 28 days of screening may undergo an additional medical assessment and/or clinical measurements to confirm their eligibility. In such instances, repeat the following screening tests and procedures:

- weight
- vital signs
- ECG
- clinical laboratory tests, and
- pregnancy test (females of childbearing potential only)

Prospective approval of protocol deviations to recruitment and enrollment criteria, also known as protocol waivers or exemptions, *is not permitted*.

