7.3. Lost to Follow-up

A participant will be considered lost to follow-up if he or she repeatedly fails to return for scheduled visits and is unable to be contacted by the study site. Site personnel or designee are

expected to make diligent attempts to contact participants who fail to return for a scheduled visit or were otherwise unable to be followed up by the site.

8. Study Assessments and Procedures

Study procedures and their timing are summarized in the SoA (Section 1.3).

Immediate safety concerns should be discussed with the sponsor immediately upon occurrence or awareness to determine if the participant should continue or discontinue study intervention.

Adherence to the study design requirements, including those specified in the SoA, is essential and required for study conduct.

All screening evaluations must be completed and reviewed to confirm that potential participants meet all eligibility criteria. The investigator will maintain a screening log to record details of all participants screened and to confirm eligibility or record reasons for screening failure, as applicable.

The specifications in this protocol for the timings of safety and sample collection are given as targets to be achieved within reasonable limits. Modifications may be made to the time points based upon emerging clinical information. The scheduled time points may be subject to minor alterations; however, the actual time must be correctly recorded in the CRF. Failure or being late (i.e. outside stipulated time allowances) to perform procedures or obtain samples due to legitimate clinical issues (for example, equipment technical problems, venous access difficulty, or participant defaulting or turning up late on an agreed scheduled procedure) will not be considered as protocol deviations but the CRU will still be required to notify the sponsor in writing via a file note.

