9.4.1. General Considerations

PK analyses will be conducted on data from all participants who receive the complete single dose of lebrikizumab and have sufficient evaluable PK data.

Safety analyses will be conducted for all enrolled participants who receive the single dose of lebrikizumab injection, whether or not they complete all protocol requirements.

Additional exploratory analyses of the data will be conducted as deemed appropriate, and study results may be pooled with the results of other studies for population PK analysis purposes to avoid issues with post hoc analyses and incomplete disclosures of analyses.

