10.9. Appendix 9: Abbreviations

Term	Definition
AD	atopic dermatitis
ADA	antidrug antibody
ADE	adverse device effect
AE	adverse event
AI	autoinjector
ALP	alkaline phosphatase
ALT	alanine aminotransferase
AST	aspartate aminotransferase
AUC	area under the concentration versus time curve
AUC(0-∞)	area under the concentration versus time curve from time zero to infinity
AUC(0-t_{last})	area under the concentration versus time curve from time zero to time t, where t is the last time point with a measurable concentration
CI	confidence interval
C_{max}	maximum observed drug concentration
complaint	A complaint is any written, electronic, or oral communication that alleges deficiencies related to the identity, quality, purity, durability, reliability, safety or effectiveness, or performance of a drug or drug delivery system.
compliance	Adherence to all study-related, good clinical practice (GCP), and applicable regulatory requirements.
CRF	case report form
CRP	clinical research physician: Individual responsible for the medical conduct of the study. Responsibilities of the CRP may be performed by a physician, clinical research scientist, global safety physician, or other medical officer.
CRU	clinical research unit
CV	coefficient of variation
device deficiencies	equivalent to product complaint
ECG	electrocardiogram
enroll	The act of assigning a participant to a treatment. Participants who are enrolled in the study are those who have been assigned to a treatment.

GCP	good clinical practice
ICF	informed consent form
ICH	International Council for Harmonisation
IEC	Independent Ethics Committee
IL	interleukin
IRB	Institutional Review Board
ISR	injection-site reaction
informed consent	A process by which a participant voluntarily confirms his or her willingness to participate in a particular study, after having been informed of all aspects of the study that are relevant to the participant's decision to participate. Informed consent is documented by means of a written, signed, and dated informed consent form.
investigational product	A pharmaceutical form of an active ingredient or placebo being tested or used as a reference in a clinical trial, including products already on the market when used or assembled (formulated or packaged) in a way different from the authorized form, or marketed products used for an unauthorized indication, or marketed products used to gain further information about the authorized form.
IWRS	interactive web-response system

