## 8. DEFINITION OF ANALYSIS POPULATIONS

The “Safety” population will consist of all participants randomly assigned to study intervention and who receive study intervention. Participants will be analyzed according to the intervention they actually received.

The “Pharmacokinetic” population will consist of all participants who received a full dose of study intervention and have evaluable PK sample.

All protocol deviations that occur during the study will be considered for their severity/impact and will be taken into consideration when participants are assigned to analysis populations.

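### Does the plan leave open whether participants who drop out before Day 22 count in the PK analysis?

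*Protocol*

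**What the plan says.** Three wordings describe who is in the PK analysis.

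- Protocol 9.3: "All enrolled participants who received a full dose of study intervention and have evaluable PK sample".
- SAP 8: the population "will consist of all participants who received a full dose of study intervention and have evaluable PK sample". It adds that protocol deviations "will be taken into consideration when participants are assigned to analysis populations".
- Protocol 9.4.1: PK analyses use "all participants who receive the complete single dose of lebrikizumab and have sufficient evaluable PK data".

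Other text bears on people who leave early.

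- Protocol 9.2 and SAP 7 let the sponsor replace early leavers: "Participants who do not complete at least through Day 22" may be replaced within their weight category. Day 22 is treated as long enough for Cmax, and Day 71 as the minimum for AUC(0-∞).
- Protocol 4.4: "Participants may be replaced to ensure that approximately 216 participants (108 in each group) complete the study".
- Protocol Appendix 9: "Participants who are enrolled in the study are those who have been assigned to a treatment".
- Protocol Section 8, on procedures missed or late for legitimate reasons, ends its examples with "participant defaulting or turning up late on an agreed scheduled procedure) will not be considered as protocol deviations".
- SAP 3 gives the SAP precedence over the protocol's statistical section and promises to flag substantial differences. SAP 11 flags only the tmax test.
- SAP 9.3.1 derives each parameter where that can be done, and says special handling of data will be documented in the study report. Most of the rest of SAP 9.3.1 and 9.3.2 is redacted.

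**The concern.** Read literally, one usable sample after a full dose admits a participant to the PK population. Someone last sampled on Day 8 and the person who replaces them would then both be in. Under Protocol 9.4.1 the first could be left out. The deviation clause in SAP 8 does not clearly help, because Protocol Section 8 takes some missed samples out of the category of deviations.

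The parameter at risk is AUC(0-tlast), because it runs to whatever sample came last. AUC(0-∞) would often be inestimable for such a person, and Cmax is usually reached early. All three parameters must meet the 0.80 to 1.25 limits. A profile that stops on Day 8 carries about a tenth of the full area. That is an extreme value on the log scale: it widens the confidence interval and, if early leaving differs by device, shifts the ratio.

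**Working it through.** **1. The plan's own figures.** Inputs from Protocol 9.2: 108 per arm, CV 30%, ratio 0.9, limits 0.80 to 1.25, 90% CI. The log SD is √ln(1.09) = 0.2936. The standard error is 0.2936 × √(2/108) = 0.0399. The distance to the nearer limit is ln(0.9/0.8) = 0.1178. Power ≈ Φ(0.1178/0.0399 − 1.652) ≈ 90%; the exact calculation gives 90.2%. Enrolment is 216/0.9 = 240. The stated figures reproduce. With all 120 per arm contributing, the standard error is 0.0379 and power is Φ(0.1178/0.0379 − 1.651) = 92.7% (92.6% by simulation).

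**2. Area in a cut-off profile.** Half-life 25 days (Protocol 4.2), so ke = ln 2/25 = 0.0277 per day. Assumed, not in the documents: one compartment, and absorption rate ka = 0.24 per day (range 0.15 to 0.40). Area to time t is proportional to (1 − e^(−ke·t))/ke − (1 − e^(−ka·t))/ka, with Day d at t = d − 1. Relative to Day 99, the area to Days 3, 5, 8, 11 and 15 is 1.2%, 4.1%, 10.1%, 16.8% and 25.7%.

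**3. Two leavers per arm, added to 120.** For Days 8, 11 and 15 the log shifts are −2.30, −1.79 and −1.36: mean −1.81, mean square 3.44, variance 0.146. The leavers' share is 2/122 = 0.0164.

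- Variance the model would estimate: 0.0862 + 0.0164 × 3.44 − (0.0164 × 1.81)² = 0.1417. The SD is 0.376 (CV 39.0%) and the standard error is 0.376 × √(2/122) = 0.0482.
- True sampling variance with equal counts per arm: 0.0862 + 0.0164 × 0.146 = 0.0886, giving a standard error of 0.0381.
- Power ≈ Φ((0.1178 − 1.651 × 0.0482)/0.0381) = Φ(1.00) ≈ 84%. Simulation gives 84.0% (81.3% to 85.9% over the absorption range).

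**4. Other cases (simulated AUC(0-tlast) power, CV 30%).** The number kept per arm is assumed.

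| True ratio | Kept per arm | Last sample Days 8–15 | Last sample Days 3–15 |
|---|---|---|---|
| 0.90 | 0 | 92.6% | 92.6% |
| 0.90 | 1 | 88.6% | 80.6% |
| 0.90 | 2 | 84.0% | 68.3% |
| 0.90 | 4 | 74.3% | 47.7% |
| 0.95 | 2 | 99.2% | 95.5% |
| 1.00 | 2 | 100% | 99.5% |

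At CV 25%, ratio 0.9 and two per arm, power is 92.2% (Days 8–15) or 75.6% (Days 3–15), against 97.9% with none. Cmax power is unchanged. At a true ratio of 1.25 the pass rate is 4.7% (2% early leavers, random counts).

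**5. What the visible text supports.** Precedence between the documents is settled: SAP 3 puts SAP 8 above Protocol 9.4.1. What is open is the meaning of *evaluable*. SAP 7 uses the word when it goes from 240 dosed to 216 with evaluable PK data by allowing for 10% who do not reach Day 71. That is not a definition, but it points away from counting a Day 8 leaver. Being in the population and having a reportable parameter are also separate steps. SAP 8 can admit a person whose AUC is then not reported, and that leaves no conflict with the sufficiency wording in Protocol 9.4.1.

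**The case for a change.** The best case for a change is that precedence selects the looser wording. SAP 8 has no sufficiency condition, so following SAP 3 leads to the reading that keeps early leavers. The SAP is also uneven within itself, since Section 7 ties evaluable data to Day 71 and Section 8 sets no follow-up. Deriving parameters where possible may remove AUC(0-∞) but does not obviously remove AUC(0-tlast), which can be computed from a short profile. The trial is open-label, so an inclusion rule is best fixed before concentrations are seen. An imbalance would hurt more: two leavers (Days 8 to 15) in the test arm only give about 66% power at ratio 0.9.

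Much of this stands as description. The terms are undefined in the visible text, and the arithmetic is right on its assumptions. It does not show that a stated rule gives a wrong result. The losses need four things together: no truncation rule in the redacted text, an analyst who keeps a profile with a tenth of the area as a valid AUC(0-tlast), several departures in the first two weeks, and a ratio near 0.9 with CV at its ceiling. The documents give no rate for leaving before Day 22; the 10% runs to Day 71. Replacement is optional. The Protocol Section 8 sentence concerns missed or late procedures, while withdrawal is dealt with in Protocol 7.2, so it says little about who enters a population.

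**Conclusion.** No change is needed. The wording is uneven and two terms are undefined, but this is a gap of detail that a PK analyst ordinarily fills parameter by parameter, and the redacted parts of SAP 9.3.1 and 9.3.2 may already fill it. If a rule is there, none of the power losses arise. The decision would not be hidden: SAP 9.1 highlights excluded participants in the listings, and SAP 9.3.1 commits to documenting special handling of data.

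If cut-off profiles were kept after all, the cost at the limiting case is about 4 points of AUC(0-tlast) power for one leaver per arm last sampled on Days 8 to 15 (92.6% to 88.6%) and about 9 points for two (to 84.0%). It is larger for Day 3 departures or an imbalance between devices. With equal numbers and the Day 8 to 15 timing, little is lost at a ratio of 0.95 or nearer 1. The balanced case costs the sponsor power and does not make a false declaration of bioequivalence more likely. These sizes rest on an assumed one-compartment profile, absorption rate, leaver count and time of last sample. The sample size is unaffected.

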9.4. Statistical Analyses

Statistical analysis of this study will be the responsibility of the sponsor or its designee.

